4.10.3.1 Complete Response (CR) Rate

CR is defined as the proportion of subjects who achieve CR, according to the response criteria for malignant lymphoma reported by the investigator ([Cheson et al 2014](#)). CR Rate will be calculated and binomial exact 2-sided CIs at 80% and 95% will be presented for subjects in the Response Evaluable Set.

4.10.3.2 Time to Response (TTR)

Time to response (TTR) is defined as the time from the first dose of study treatment to the first documented objective response. TTR data will be listed and summarised in subjects who achieved an objective response. $TTR \text{ (months)} = (\text{date of first objective response} - \text{date of first dose} + 1) / (365.25/12)$.

Only subjects who have achieved objective response (CR or PR) are evaluated for TTR.

Subjects who discontinue study treatment without a response or progression, receive a subsequent anti-cancer therapy, and then respond will not be included (ie, the visit contributing to a response must be prior to subsequent therapy for the subject to be considered as a responder).

If numbers of responders allow, the median TTR and two-sided 95% CI will be assessed using the Kaplan-Meier method (without censoring because all subjects have events). The number of subjects with response at different disease assessment timepoints may be provided.

4.10.3.3 Duration of Response (DoR)

DoR is defined as the time from the first objective response to the time of documented disease progression or death due to any cause, whichever occurs first.

$DoR \text{ (months)} = (\text{date of PFS event (progression/death) or censoring} - \text{date of first objective response} + 1) / (365.25/12)$

The end of response should coincide with the date of progression or death from any cause used for the PFS endpoint. The time of the initial response is defined as the latest of the dates contributing towards the first visit response of CR or PR. If a subject does not progress following a response, then their DoR is censored on the PFS censoring date. Only subjects who have achieved objective response are evaluated for DoR.

Individual duration of treatment and duration of response will be appropriately presented in a swimmer plot (including non-responders subjects) and all response assessments performed by the investigator will be displayed.

Only subjects who have achieved objective response (CR or PR) are included in the summaries of DoR. If numbers of responders allow, Kaplan-Meier plots of DoR will be presented. The median DoR and 2-sided 80% and 95% CIs will be estimated using the Kaplan-Meier method.

4.10.3.4 Progression-free Survival (PFS)

Disease progression will be determined by the investigators according to the revised response criteria for malignant lymphoma ([Cheson et al 2014](#)).

PFS is defined as the time from first dose date to documented disease progression, or death (from any cause in the absence of progression), regardless of whether the subject withdraws from therapy or receives another anti-cancer therapy prior to progression.

PFS (months) = (date of PFS event (progression/death) or censoring – first dose + 1) / (365.25/12)

Subjects who are progression free and alive at the time of data cut-off, or have unknown status, will be censored at the time of the latest date of assessment from their last evaluable disease assessment. However, if the subject progresses or dies immediately after two or more consecutive missed visits, the subject is censored at the time of the latest evaluable disease assessment prior to the two missed visits. Note: a NE visit is not considered as a missed visit.

Given the scheduled visit assessment scheme (ie, 9-weekly for the first 26 weeks then 12-weekly thereafter), the definition of 2 missed visits will depend on the scheme.

If the previous assessment is less than study day 113 (ie, week 16) then 2 missing visits will equate to 20 weeks since the previous assessment, allowing for early and late visits (ie, 2×9 weeks + 1 week for an early assessment + 1 week for a late assessment = 20 weeks).

If the 2 missed visits occur over the period when the scheduled frequency of assessment changes from nine-weekly to twelve-weekly this will equate to 23 weeks (ie, take the average of 9 and 12 weeks which gives 10.5 weeks and then apply the same rationale, hence 2×10.5 weeks + 1 week for early assessment + 1 week for late assessment = 23 weeks). The time period for the previous assessment is from study days 113 to 175 (ie, week 16 to week 25).

From week 25 onwards (when the scheduling changes to 12-weekly assessments), two missing visits equates to 26 weeks (ie, 2×12 weeks + 1 week for an early assessment + 1 week for a late assessment = 26 weeks).

If the subject has no evaluable disease assessments post-baseline or does not have baseline tumour assessment data they are censored at Day 1 unless they die within two visits of baseline (8 weeks plus 9 weeks plus 1 week allowing for a late assessment within the visit window) when the death date qualifies as a PFS event.

A summary of censoring rules and the date of PD/death or censoring are given in [Table 4](#). Note that censoring overrides event in certain specified cases.

Table 4 Summary of Censoring Rules for PFS

Situation	Date of PD/Death or Censoring	PFS Outcome
Documented Progressive Disease (PD) or death in the absence of progression	Date of earliest documentation of PD or date of death in the absence of progression	Event
Either no tumour assessment at baseline or no evaluable assessments post-baseline	Date of death	Event

Table 4 Summary of Censoring Rules for PFS

Situation	Date of PD/Death or Censoring	PFS Outcome
AND death prior to second scheduled post-baseline disease assessment		
Either no tumour assessment at baseline or no evaluable assessments post-baseline AND no Death prior to second scheduled post-baseline disease assessment	Date of first dose (Day 1)	Censored
PD or death (in the absence of progression) immediately after ≥ 2 consecutive missed disease assessments as per the protocol specified assessment schedule	Last evaluable progression-free disease assessment prior to missed assessments	Censored
On-going with neither PD nor death at the time of analysis or lost to follow-up or withdrawn consent	Date of last evaluable disease assessment	Censored

Abbreviations: PD = progressive disease; PFS = progression-free survival.

The PFS time is always derived based on scan/assessment dates, not visit dates.

Disease assessments/scans contributing towards a particular visit may be performed on different dates. The following rules are applied:

- The date of progression is determined based on the earliest of the dates of the component that triggered the progression.
- When censoring a subject for PFS the subject is censored at the latest of the dates contributing to a particular overall visit assessment.

Note: for target lesions only the latest scan date is recorded out of all scans performed at that assessment for the target lesions and similarly for non-target lesions only the latest scan date is recorded out of all scans performed at that assessment for the non-target lesions

The main analysis of PFS is based on the FAS. The number and percentage of subjects experiencing a PFS event [broken down by type of event/censoring] and Kaplan-Meier plots of PFS will be presented. The median PFS and its 2-sided 80% and 95% confidence intervals will be estimated using the Kaplan-Meier method (if subject numbers allow).

The treatment status of subjects at progression will be summarised. This includes the number (%) of subjects who were on study treatment at the time of progression, the number (%) of subjects who discontinued study treatment prior to progression, the number (%) of subjects who did not progress and were on treatment or discontinued treatment.

A summary of the duration of follow-up for PFS will be included using median range for censored subjects (including all types of PFS censoring).

Duration of follow-up for PFS is applicable only for PFS censored subjects and is defined as follows:
Duration of follow-up for PFS (months) = (date of PFS event (progression/death) or censoring – date of first dose + 1) / (365.25/12).

The proportion of subjects progression free at every 3 months (3, 6, 9, 12, etc.) and associated 2-sided 80% and 95% CIs will be estimated using Kaplan Meier method.

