4.3.2 Visit Window

For safety and tumour assessments, visit windows will be defined for any presentations that summarise values by visit. The following conventions will apply:

For tumour assessments:

- The protocol assigned windows for tumour assessments will be used to assign the result to a particular visit.
- For example, the visit windows for tumour assessments are:
 - After 8 weeks: 49-63
 - After 17 weeks: 112-126
 - After 26 weeks: 175-189

For safety assessments:

- The time windows will be exhaustive so that data recorded at any timepoint has the potential to be summarised. Inclusion within the time window will be based on the actual date and not the intended date of the visit.
- All unscheduled visit data will have the potential to be included in the summaries.
- The window for the visits following baseline will be constructed in such a way that the upper limit of the interval falls halfway between the two visits (the lower limit of the first post-baseline visit will be Day 2). If an even number of days exists between two consecutive visits then the upper limit will be taken as the midpoint value minus 1 day.
- For example, the visit window for AZD4573 administration (with 1 week between scheduled visits) are:
 - Cycle 1 6 mg AZD4573 Dose 1:1
 - Cycle 1 9 mg AZD4573 Dose 1: 2-11
 - Cycle 1 12 mg AZD4573 Dose 1: 12-18
 - Cycle 1 12 mg AZD4573 Dose 2: 19-25
 - Cycle 1 12 mg AZD4573 Dose 3: 26-32

- If dose delays are experienced, the planned dosing visit windows will be modified during the programming to anchor to the actual visit date where intervention was administered on to adjust for these dose delays. The same rules apply to safety visits of other types (non-dosing visits) where the safety visit is moved due to a dose delay. For example, if the Day 8 dose is taken on Day 10, the visit windowing will be anchored around Day 10 for this visit.
- Visit windowing will be done separately for each assessment based on the schedule of events specific to that assessment.
- Should Study Day be missing (due to partial or missing dates), then visit will be assigned to the nominal visit at which that assessment was recorded, and no windowing will be performed.
- For summaries showing the maximum or minimum values, the maximum/minimum value recorded on treatment (from the day of the first IP administration up to the day of the last IP administration) will be used (regardless of where it falls in an interval).

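### The two-missed-visits PFS rule makes no provision for a baseline scan, so it can censor a progression after one missed scan or date the censoring before Day 1

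*SAP*

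**What the plan says.** SAP 4.10.3.4 censors a PFS event "if the subject progresses or dies immediately after two or more consecutive missed visits". Scans are "9-weekly for the first 26 weeks then 12-weekly thereafter", and the rule is applied through three elapsed-time tiers:

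- **Tier 1:** "If the previous assessment is less than study day 113 (ie, week 16) then 2 missing visits will equate to 20 weeks".
- **Tier 2:** 23 weeks. "The time period for the previous assessment is from study days 113 to 175 (ie, week 16 to week 25").
- **Tier 3:** 26 weeks, from week 25 onwards.

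Table 4 gives the censoring date for these cases as "Last evaluable progression-free disease assessment prior to missed assessments". Censoring at Day 1 is reserved for subjects with no baseline tumour assessment or no evaluable post-baseline assessment. For those subjects a death counts as an event if it falls within 8 + 9 + 1 weeks.

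SAP 4.3.2 gives the scan windows as "After 8 weeks: 49-63", "After 17 weeks: 112-126" and "After 26 weeks: 175-189". SAP 4.3.1 sets first dose as Day 1, with no Day 0. SAP 4.10.3.5 (target lesion size) takes baseline as the last evaluable assessment before treatment starts.

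**The concern.** The tiers are built for intervals between post-baseline scans. When the previous assessment is the baseline scan, three things go wrong or are left open:

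- The clock starts before first dose, so screening days count towards the limit. A progression after one missed scan can then be treated as if two had been missed.
- The censoring date in Table 4 has no floor at Day 1. A subject whose first post-baseline scan shows progression at Week 26 has an evaluable post-baseline scan, so the Day 1 row does not apply and the censoring date falls before treatment.
- The tier boundaries and the scan windows do not meet on the same day, so a scan on the boundary may be given the wrong limit.

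At stake are the event or censoring status of individual subjects and the censored-subject follow-up summary, which uses the same formula and could print a negative minimum. Where a response came first, a boundary-day case would also carry into DoR, because 4.10.3.3 uses the PFS event or censoring date. The baseline cases cannot affect DoR, since no response precedes them.

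**Working it through.** **1. The plan's own limits.** 2×9+2 = 20 weeks = 140 days; 2×10.5+2 = 23 weeks = 161 days; 2×12+2 = 26 weeks = 182 days. All three reproduce.

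**2. Baseline scan, only Week 8 missed, progression in the Week 17 window (Days 112-126).** With the baseline scan on Day -k, the gap is (PD day - 1 + k) and the limit is 140 days. The SAP does not give the lead time k, so a range is shown. The limit is taken as strictly exceeded.

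| Baseline scan | Gap, Day 112 to Day 126 | PD days censored |
|---|---|---|
| Day -15 | 126 to 140 | 0 of 15 |
| Day -16 | 127 to 141 | 1 of 15 (Day 126) |
| Day -21 | 132 to 146 | 6 of 15 (Days 121-126) |
| Day -28 | 139 to 153 | 13 of 15 (Days 114-126) |

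**3. Baseline scan, Weeks 8 and 17 missed, progression at Week 26 (Days 175-189).** The smallest gap, from Day -1 to Day 175, is 175 - 1 + 1 = 175 days. This exceeds 140, so the subject is always censored, and Table 4 points to the baseline scan. PFS = (-k + 1)/(365.25/12) = (-k + 1)/30.4375 months:

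- Day -1: 0.00
- Day -7: -6/30.4375 = -0.20
- Day -14: -13/30.4375 = -0.43
- Day -28: -27/30.4375 = -0.89

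**4. Day scale.** The 4.3.2 windows are weeks × 7 ± 7: 119 ± 7 = 112-126 and 182 ± 7 = 175-189. With first dose as Day 1, the same visits on the study-day scale are 113-127 and 176-190, which match tier boundaries at 113 and after 175. Week 38 and Week 50 windows are not stated; ±7 days is assumed.

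- If the 4.3.2 windows are study days, a Day 112 scan is a Week 17 scan held to 140 days. With only Week 26 missed and PD at Week 38 (Days 259-273), the gap is 147 to 161 days, censored on 15 of 15 days.
- A Day 175 scan with only Week 38 missed and PD at Week 50 (Days 343-357) gives 168 to 182 days. All are censored under the 161-day tier and none under the 182-day tier. Both tiers mention week 25.
- If the windows are 50-64, 113-127 and 176-190, the largest gaps with one missed scan are 190-50 = 140, 274-113 = 161 and 358-176 = 182. These equal the limits, so none is censored.

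**5. Strict or not.** The text does not say whether the gap must exceed the limit or only reach it. If reaching it is enough, the pair Day 49 to Day 189 (140 days) is censored after one missed scan.

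**The case against.** The strongest objection concerns the day scale. A reader might infer that progressions following a Day 112 or Day 175 scan and one missed visit are always wrongly censored, and that the PFS tiers are at fault. The documents do not support that. The tiers fit the SAP's study-day convention exactly, so the one-day slip more likely sits in the 4.3.2 windows. Those windows are introduced as examples for by-visit presentations, while PFS is derived from scan dates. Day 175 can be read into either of two tiers, so its outcome is ambiguous rather than fixed. What stands is that the two sections need reconciling.

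On the baseline cases, it can be said that the lead time is not in the SAP, that Table 4 asks for at least two consecutive missed assessments, and that a baseline scan is not naturally called progression-free. The first point is why a range is shown. On the second, the elapsed-time definition is the plan's only stated way of counting missed visits, and it conflicts with Table 4 in exactly these cases. If the third is accepted, the plan gives no censoring date at all for the Week 26 case, so a sentence is needed either way.

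A reader might also infer a material upward bias in PFS. A subject censored at Day 1 adds nothing to the Kaplan-Meier product, so dropping a negative time or moving it to Day 1 gives essentially the same curve. A time of exactly zero is admissible. The effect of the non-positive times is mainly on counts, numbers at risk and the follow-up range. This objection stands.

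**Conclusion.** The rule fails for a baseline scan on the text as written. One missed scan can be scored as two once the baseline scan is at least 16 days before first dose, on 1 to 13 of 15 Week 17 window days for lead times of 16 to 28 days. Two missed scans followed by progression at Week 26 give a PFS time of zero or below. These results assume a strictly exceeded limit, the 4.3.2 windows taken as study days, and a lead time the SAP does not state. If the Week 17 window is Days 113-127, the onset moves to Day -15 (127 - 1 + 15 = 141).

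The day-scale mismatch is a smaller matter of consistency between two sections.

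Few subjects are likely to be affected. PFS is secondary in Module 1 Part B and exploratory elsewhere, and no hypothesis is tested (4.10.1). The one-missed-scan errors do all run in one direction, turning progressions into censored times, and 4.10.3.4 specifies no sensitivity analysis that would show them. The correction is worth making because it is nearly free, not because it would move the PFS estimate much.

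**What to change.** In 4.10.3.4 and Table 4:

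- State that where the previous assessment is the baseline scan, time is counted from Day 1, the 18-week (126-day) limit from the plan's own 8 + 9 + 1 weeks applies, and censoring is at Day 1.
- State that the gap must exceed the limit.
- Assign the boundary day to one tier only.

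Put 4.3.2 and 4.10.3.4 on the same day scale. Either write the windows as 113-127 and 176-190 (with Week 8 as 50-64) and keep the present tiers, or keep the windows and cut the tiers at 112 and 175 (before 112; 112-174; 175 onward). With either choice and a strict limit, no progression after one missed post-baseline scan is censored.

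The baseline sentence works on both scales. The latest Week 17 scan is 125 days (Day 126) or 126 days (Day 127) after Day 1, neither above 126. The earliest Week 26 scan, on Day 175, is 174 days after Day 1 and is still censored, with PFS = 1/30.4375 = 0.03 months instead of a negative value.

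The cost is a few sentences in the SAP and a few lines in the PFS derivation, with no new data.

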The analysis of OS is based on the FAS. The number and percentage of subjects experiencing an OS event and Kaplan-Meier plots of OS will be presented. If subject numbers allow, the median OS and 2-sided 80% and 95% CI will be estimated using the Kaplan-Meier method.

Summaries of the number and percentage of subjects who have died, those still in survival follow-up, those lost to follow-up and those who have withdrawn consent will be provided.

A summary of the duration of follow-up for OS will be included using median (range). This will be presented separately for censored and non-censored subjects.

Duration of follow-up for OS is reported separately for censored subjects and non-censored subjects and is defined as follows:

Duration of follow-up for OS (months) = (date of death or censoring (date last known to be alive) – date of first dose + 1) / (365.25/12).

The proportion of subjects alive at every 3 months (3, 6, 9, 12) and associated 2 sided 80% and 95% CIs will be estimated using the Kaplan-Meier method.

Supportive data: Change in Target Lesion Tumour Size

Target lesions are measurable tumour lesions. Baseline is defined to be the last evaluable assessment prior to starting treatment.

Target lesion tumour size for the target measurable nodes and extra-nodal sites at any timepoint is defined as the sum of the product of the perpendicular diameters for multiple lesions. When a lesion is too small to measure, 5 mm x 5 mm will be assigned as the product of the perpendicular diameters.

If target lesion measurements are missing post-baseline, then the sum of the product of perpendicular diameters for multiple lesions will be set to missing for that post-baseline measurements. Subsequent percentage changes will consequently not be calculated using post-baseline measurements where any target lesion measurement is missing.

The percentage change in target lesion size at each timepoint for which data are available will be obtained for each subject, taking the difference between each timepoint and baseline multiplied by 100 (ie, [timepoint – baseline]/baseline x 100).

The best change in tumour size from baseline (ie, depth of response) is the largest decrease from baseline or the smallest increase from baseline in the absence of a reduction and includes all assessments:

- up to and including the first visit at which the overall visit response is a PD,
- prior to death in the absence of progression,

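### Median PFS follow-up is taken in censored subjects only, Day 1 censoring included, so it varies with the event rate and missing scans and can understate Module 1 follow-up

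*SAP*

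**What the plan says.** SAP section 4.10.3.4 plans a summary of PFS follow-up "using median range for censored subjects (including all types of PFS censoring"), and then repeats the restriction: "Duration of follow-up for PFS is applicable only for PFS censored subjects and is defined as follows". The formula is "Duration of follow-up for PFS (months) = (date of PFS event (progression/death) or censoring – date of first dose + 1) / (365.25/12"). It names the event date although subjects with events are excluded.

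The same section and its Table 4 decide which dates enter:

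- Subjects with no evaluable post-baseline assessment, or no baseline assessment: "they are censored at Day 1 unless they die within two visits of baseline". Table 4 gives the censoring date as "Date of first dose (Day 1").
- Subjects whose progression or death follows two or more consecutive missed assessments are taken back to the last evaluable assessment before the gap.
- Subjects still progression-free are censored at their last evaluable assessment, not at the data cut-off.

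PFS is analysed in the FAS, so subjects without scans stay in. Table 1 (section 3.2) sets the Module 1 primary cut-off at about 6 months after last subject first dose or at 75% progressed or died, whichever is first. For survival, section 4.10.3.5 differs: "Duration of follow-up for OS is reported separately for censored subjects and non-censored subjects".

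**The concern.** Median follow-up tells the reader how far the PFS curve and the 3-monthly progression-free proportions can be trusted. A median among censored subjects answers another question. Subjects enrolled early have had the longest time in which to progress, so they tend to leave the summary, and those remaining are disproportionately recent. The figure therefore falls when the disease is faster, even if every subject entered on the same dates and the cut-off is unchanged.

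Day 1 and back-dated censoring add a second problem. Those dates record missing scans, not the time for which a subject was observed. With a cut-off at 75% events, about a quarter of a small cohort may be left censored, so a few such dates can move the median. At stake is a misreading of data maturity, not a wrong PFS estimate.

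**Working it through.** The SAP states no follow-up figure, so there is none to reproduce.

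**1. What each censoring date contributes.** The divisor is 365.25/12 = 30.4375 days per month.

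| Censoring date | Calculation | Months |
|---|---|---|
| Day 1 | (0 + 1)/30.4375 | 0.03 |
| Week 8 | (56 + 1)/30.4375 | 1.87 |
| Week 17 | (119 + 1)/30.4375 | 3.94 |
| Week 26 | (182 + 1)/30.4375 | 6.01 |
| Week 38 | (266 + 1)/30.4375 | 8.77 |

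**2. How many Day 1 subjects it takes** (the others censored at week 26):

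- 3 at Day 1 and 5 at week 26: median 6.01, no effect.
- 4 and 4: (0.03 + 6.01)/2 = 3.02.
- 5 and 3: median 0.03, one day.

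A one-day result therefore needs more than half of the censored subjects at Day 1.

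**3. Worked example at the 75% trigger** (assumed). Twenty subjects: 15 events by week 17, 3 censored at Day 1, 2 at week 26.

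- Plan's rule: the median of 0.03, 0.03, 0.03, 6.01, 6.01 is 0.03 months.
- Reverse Kaplan-Meier, all 20 subjects: at Day 1, 1 − 3/20 = 0.85. The 15 events leave without a step. At week 26, 0.85 × (1 − 2/2) = 0. The median is 6.01 months.

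**4. The event-rate effect without Day 1 cases.** Assume potential follow-up uniform on 6 to 18 months (true median 12), exponential PFS with median m, and no scan schedule. The censored share is [m/(12 ln 2)] × (2^(−6/m) − 2^(−18/m)). The censored-only median x solves 2^(−x/m) = (2^(−6/m) + 2^(−18/m))/2.

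- m = 6: censored share 0.721 × (0.5 − 0.125) = 0.27, so 73% events. 2^(−x/6) = 0.3125, so x = 10.1, which is 1.9 months short.
- m = 3: 91.5% events, x = 8.7.
- m = 2: 97% events, x = 8.0.

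Only m = 6 is compatible with the 75% trigger. With 5% of subjects set to Day 1 in that case, the plan's median is 9.1 against 11.7 by reverse Kaplan-Meier.

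**5. Simulation with the plan's scan schedule and 75%/6-month cut-off.** Sample size, accrual, PFS and the unassessed share are all assumed.

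- N of 15 or 30, 12-month accrual, median PFS 2 to 6 months, 0 to 10% unassessed: typical gaps to reverse Kaplan-Meier ran from about 0 to 6 months, mostly 1 to 4. The reverse Kaplan-Meier median was not estimable in 0 to 49% of runs.
- A second set-up used 12 or 18 months of accrual, no cut-off before accrual ended and no unassessed subjects. The plan's statistic was typically 1.87 to 8.77 months and reverse Kaplan-Meier 8.77 to 14.29, a gap of 2.8 to 6.9. This set-up compares medians across runs and drops runs in which reverse Kaplan-Meier was not estimable.

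The direction is the same in both. The size depends on the set-up.

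**The case against.** The statistic is openly labelled as censored-only, is computable, and is accompanied by a range. Section 4.10.3.4 also breaks PFS outcomes down by type of event and censoring, so the Day 1 count is largely planned already. No hypothesis is tested (section 4.10.1), and no PFS or DoR estimate changes. All of this stands and limits the weight of the point.

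Reverse Kaplan-Meier is not free of trouble either. It uses the same Day 1 and back-dated dates, so it reduces their effect without removing it. It also relies on the same few censored subjects. Under the uniform 6 to 18 month assumption, its median was not estimable at N = 30 in 55% of runs with median PFS 2 months and 27% with 3 months. At N = 15 the shares were 69% and 38%. This stands too, and is why a fallback is needed.

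A reader might infer three stronger things, which the SAP does not support:

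- **A one-day median is the likely result.** It needs a majority of censored subjects at Day 1, and the rule that counts deaths within 8 + 9 + 1 = 18 weeks as events limits their number.
- **A shortfall of 4 months (8.0 against 12.0) is the norm at the primary analysis.** That case has 97% events, past the 75% trigger. A later final analysis could be that mature, but section 3.2 makes the primary analysis final on early termination, and section 4.12 records that enrolment was permanently halted.
- **OS follow-up has the same defect.** It is reported for both censored and non-censored subjects, and Day 1 censoring for missing scans is a PFS rule only.

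**Conclusion.** The point holds for Module 1 PFS as a weakness in a descriptive statistic. As defined, median follow-up moves with the event rate and with missing scans, and it can understate the time for which subjects were followed. At the plan's own cut-off the shortfall is typically 0 to 4 months, assuming 15 to 30 subjects, 12 months of accrual and median PFS of 2 to 6 months. Other plausible set-ups give more, so this is an order of magnitude, not an estimate for this trial. It falls to one day only where Day 1 subjects are more than half of those censored.

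The formula's reference to an event date is a separate drafting slip. Module 2 is unaffected in practice: section 4.14 limits its three treated subjects to listings and figures.

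**What to change.** In SAP section 4.10.3.4:

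1. Report median PFS follow-up in all FAS subjects by reverse Kaplan-Meier, with censoring as the event and PFS events as censored.
2. Also report the median (range) time from first dose to data cut-off, to be used when the reverse Kaplan-Meier median is not estimable. It does not depend on events or scans, but it ignores dropout and should be labelled as potential follow-up.
3. Show the number censored at Day 1 beside these figures.
4. Keep the censored-only median and range as a labelled supplement, and delete the reference to a PFS event date from its formula.

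The cost is a short text change and one extra descriptive output from data already held, which may be not estimable in small cohorts. PFS estimates and confidence intervals stay as they are, and section 4.10.3.5 on OS needs no change.
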